# FIGURE 2: The one-dimensional pain intensity scales: the NRS, the VAS and the four-point VRS (45)

The patients with malignant pleural effusion will have pleurodesis done once full lung re-expansion is confirmed by chest radiograph.

The criteria for chest tube removal will include:

- Improved or resolution of the clinical condition
- Change of effluent to serous fluid for all types of pleural fluid collections or cessation of air leak for pneumothorax
- Reduction of volume of daily effluent to less than 100ml in a 24-hour day period
- Evidence of full lung re-expansion on the most current chest radiograph
  - 4) Procedure for chest tube removal

The chest tube will only be removed after satisfactory confirmation by the principal investigator or atleast a senior resident doctor in the unit, that the conditions above have been fulfilled. The chest tube will be removed by two members of the team, one of which must be atleast a senior resident doctor that has been adequately exposed to this protocol.

For patients who had purse-string placement in Group A, the integrity of the suture is first checked to be sure that it is intact, then the anchor stitches are then cut at the limbs to release it from the skin. The chest tube is checked that it is free of attachments to the skin after which the patient is then instructed to make a full inspiratory effort and thereafter arrested expiration. For unconscious patients on ventilator, the intensivist will give a Valsalva manoeuvre of 35 to 40cm H2O to achieve full inspiration and retains that pressure during the tube removal to simulate arrested expiration.

The lead surgeon (principal investigator or senior resident doctor) makes a surgeon's knot with the purse string without tying it down or snug in preparation for a brisk removal of the chest tube by the

assistance. To ensure synchrony, a short count of one to three is done by the lead surgeon and by the count of three, he completes the knotting down to close the wound just as the tube is rapidly pulled out at a single swipe by the assistance upon completion of the count of three. There will be regular rehearsals and practice of these synchronous actions by all those who will be involved with this study as surgeons and assistants. The wound must be closed to air and water tightness but without strangulating the edges. The suture is trimmed, and a sterile dressing applied as before. There will be strict observance of aseptic technique by all involved in this tube removal process. A chest radiograph is done immediately after to check for presence of iatrogenic pneumothorax. The wound dressing will be removed on the third day and subsequent wound care will be determined by the finding at wound review by the principal investigator on this third day. The protocol to follow will be to continue daily povidone iodine wound care if there is evidence of wound infection but to leave the wound open to fresh air and apply povidone iodine topical cream till the suture is removed by day 7, after tube removal. The pain score will be assessed on a continuous basis (everyday till patient is discharged home and at every contact in the outpatient clinic). The patients will be followed up once a month for atleast 3 consecutive months after chest tube removal. Their pain score, wound outcomes and serial chest radiographic check (immediately after tube removal, at one week after tube removal and at every follow up visit in the outpatient clinic), will be done.

For Group B patients who did not have a purse-string placed during chest tube insertion, the anchor stitches are the cut at the limbs to release it from the skin. The chest tube is checked that it is free of attachments to the skin, the patient is then instructed to make a full inspiratory effort and thereafter arrest expiration. For unconscious patients on ventilator, the intensivist gives a Valsalva manoeuvre of 35 to 40cm H2O to achieve full inspiration and retains that pressure during the tube removal to simulate arrested expiration. Following the model of synchronized action between two surgeons as described above for Group A patients, the lead surgeon applies the Primapore occlusive-adhesive dressing firmly at the count of three immediately after the assistant has pull out the chest tube from the pleural space in brisk but in a measured fashion. The occlusive dressing is retained for a atleast three (3) days to allow the wound to seal before it is either changed or removed depending on the wound condition. This decision will be taken by the principal investigator. The protocol to follow will be to change the dressing if the wound is not completely sealed after 3days but to leave it open to fresh air with topical application of povidone iodine cream. If there is evidence of wound infection, the dressing will be done using 10% povidone iodine solution and a sterile gauze. A chest radiograph is done to assess for the presence of pneumothorax (immediately after chest tube removal, at one week after removal and at every outpatient clinic visit). The patients are followed up for once a month for atleast 3 consecutive months after chest tube removal.

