#### **STUDY SUMMARY**

Title: Suturing with U-Technique versus Un-Reapproximated wound Edges during removal of Closed Thoracostomy-tube drain - A single centre Open-label randomized prospective trial (SUTURE TRIAL)

**Background:** Closed thoracostomy tube drainage or chest tube insertion is one of the most commonly performed procedures in thoracic surgery. There are several published evidence-based guidelines on safe performance of a chest tube insertion. However, there is absence of prospective controlled trials or systematic reviews indicating the safest technique of closing the wound created at the time of chest tube insertion and that best guarantees good wound and overall outcomes, post-chest tube removal. The use of a horizontal mattress non-absorbable suture or U- suture which is placed at the time of chest tube insertion and used to create a purse-string wound re-approximation at the time of tube removal has been an age-long and time-honored practice in most thoracic surgical settings. It has been established by a recent study that an occlusive adhesive-absorbent dressing can also be safely used to occlude the wound at the time of chest tube removal with good wound and overall outcomes though the study focused on tubes inserted during thoracic surgical operations.

Research Design: The study is an Open-label randomized prospective trial

**Methodology:** 142 consenting patients with indication for chest tube insertion, who meet the inclusion criteria for enrolment in the study will be randomly assigned into two balanced groups- Group A; that will have a Prolene 1 purse-string suture placed around the thoracostomy wound at the time of chest tube insertion and which will be used for the thoracostomy wound closure at the time of chest tube removal and Group B, that will not have a purse-string suture placement during chest tube insertion and will have their wounds covered by an occlusive adhesive-absorbent dressing material (Primapore\*), at the time of chest tube removal care and outpatient follow-up; will be similar for both groups and will follow a pre-determined standardized protocol. Specific clinical outcomes while the chest tube is indwelling and specific clinical and wound outcomes after the chest tube removal will be observed in both Groups for comparison and to determine causal relationships. Observations will be recorded in a specially-designed study proforma.

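### Group A has assured wound contact by day 7 while Group B has only a film named at one week, and neither arm has an explicit, dated one-week wound assessment

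*Combined protocol and SAP*

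**What the plan says.** The Study Summary states that care and outpatient follow-up "will be similar for both groups and will follow a pre-determined standardized protocol". The detail is in Chapter Three, Procedure for chest tube removal, which has a separate paragraph for each arm.

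**Group A (suture).** "The wound dressing will be removed on the third day and subsequent wound care will be determined by the finding at wound review", and this is a "wound review by the principal investigator on this third day". If there is no infection, the instruction is to "apply povidone iodine topical cream till the suture is removed by day 7, after tube removal". The paragraph then lists the follow-up content: "Their pain score, wound outcomes and serial chest radiographic check (immediately after tube removal, at one week after tube removal", with outpatient visits completing the bracket.

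**Group B (dressing).** "The occlusive dressing is retained for a atleast three (3) days to allow the wound to seal before it is either changed or removed". On that choice, "This decision will be taken by the principal investigator". The one-week item is a film with a stated purpose: "A chest radiograph is done to assess for the presence of pneumothorax (immediately after chest tube removal, at one week after removal", again with outpatient visits completing the bracket. Wound outcomes and pain score are not named at one week.

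**Both arms.** Follow up and treatment adherence sets monthly visits for at least three months, covering wound infection, pain, film and scar. The Study Proforma is the same for everyone. Item 35 has yes/no boxes for infection, dehiscence, fluid leakage and air suck-in after removal, and pain scores twice daily for days 1 to 10. The only field in it tied to one week is the radiograph.

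**The concern.** Early complications after removal are one of the three specific objectives, and wound infection and dehiscence are listed dependent variables. Infection is defined mainly by discharge from the wound, which can come and go between visits, so recording it depends on somebody looking. If one arm is sure of a wound contact at about day 7 and the other is not, recorded early event rates can differ when the true rates do not. The contact falls to the suture arm, so the likely direction is fewer recorded events in the dressing arm. The same gap could hide harm from the dressing.

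Two features make this hard to repair afterwards. With no date on the item 35 wound boxes, a NO does not show whether or when the wound was examined. And Data Analysis and Management plans a Cox analysis of complications, which needs event times; for events found by inspection, those times depend on when inspection took place.

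**Working it through.** The plan contains no figure for ascertainment, so there is nothing to reproduce. The check is a side-by-side reading of the removal procedure, the follow-up section and the proforma.

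| Time after removal | Group A | Group B |
|---|---|---|
| Immediately | Film | Film |
| Day 3 | Dressing off, wound reviewed by the principal investigator | Dressing on for at least 3 days, then changed or removed on the principal investigator's decision; no upper limit stated |
| By day 7 | Suture removed | No wound contact stated |
| One week | Film; pain score and wound outcomes named in the same sentence, timing ambiguous | Film only |
| Monthly, at least 3 visits | Infection, pain, film, scar | Same |
| Item 35 wound boxes | Undated | Undated |

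1. **Day 3.** The arms are nearly parallel. The Group B instructions depend on whether the wound has sealed and whether it is infected, so it has to be looked at, and the same person decides. The difference is that Group A's day is fixed and Group B's is a minimum.
2. **Around day 7.** This is where the arms part. Suture removal in Group A cannot be done without seeing the wound. Group B has no counterpart.
3. **The Group A sentence on wound outcomes.** Its bracket containing one week directly follows the radiographic check. The Group B paragraph attaches nearly the same bracket to the film alone. The one-week timing may therefore apply only to the film in Group A as well.
4. **Later capture.** The follow-up forms ask about infection and dehiscence but have no box for fluid leakage. After removal, leakage appears only in item 35, so no later form has a field for a leak missed early.
5. **What is not affected.** The film times are the same in both arms, so this point does not touch pneumothorax, the outcome used for the sample size. Pain has fields for days 1 to 10 in both arms.

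**Direction only.** Inputs: 71 per arm (Sample Size) and a 7.7% wound infection risk (Literature Review), taken as equal in both arms. Assume Group A records every infection and Group B records a share s of them. Expected records are 71 × 0.077 = 5.5 in Group A and 5.5 × s in Group B:

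- s = 0.9: 4.9, a difference of about 0.5 patients
- s = 0.7: 3.8, a difference of about 1.6 patients
- s = 0.5: 2.7, a difference of about 2.7 patients

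The apparent ratio of A to B is 1/s (1.11, 1.43, 2.0), so the calculation returns whatever was assumed. The documents give no value for s. The figures show which way the error would run and that it amounts to a few patients at most under these assumptions; they do not estimate it.

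**The case against.** The strongest reply is that a good deal is common to both arms. The principal investigator judges Group B wounds once the dressing has been on for at least three days. Group B has a film at one week, and nothing stops the team from looking at the wound then. Item 35 asks every patient the same questions, and the monthly checks are identical. Group B wounds that have not sealed get a dressing change, which is an extra contact for problem wounds. All of this stands, and it limits the gap mainly to patients already discharged by one week.

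A reader might infer that a one-week wound assessment is scheduled for Group A alone, or that complications are deliberately sought harder in the suture arm. The documents support neither. Suture removal is a treatment step with no assessor, outcome or record attached, and the one-week bracket is ambiguous. Nor does it follow that a Group B wound discharging on day 6 would be recorded as free of infection, since the film is due at one week. Air suck-in adds little here: it is recorded under complications immediately after removal, and nothing links its detection to day 7.

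The reply does not remove the remaining gap. A shared form fixes what is asked, not when the wound is examined. An inspection that is possible at the film visit but not written down may happen in one arm and not the other.

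**Conclusion.** The point holds as a moderate and easily corrected weakness. Followed as written, the plan assures wound contact by day 7 in Group A and specifies none in Group B at that time. Neither arm has an explicit one-week wound outcome assessment, and the early wound fields are undated. This allows unequal ascertainment of early infection, dehiscence and fluid leakage in an open-label comparison, probably in favour of the dressing.

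The conclusion assumes that suture removal leads staff to notice and record wound problems, and that some Group B patients will have been discharged and will have a film without a wound inspection. The documents settle neither. The size is unknown. The Study Summary's statement of similar follow-up shows the intention but does not supply the missing schedule.

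**What to change.** Reconcile the two arm paragraphs under Procedure for chest tube removal, the section Follow up and treatment adherence, and proforma item 35 into one outcome-assessment schedule that applies to both arms:

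- a wound check when the dressing is first changed or removed (from day 3), with the day recorded;
- a wound check at the existing one-week film visit, recorded for every patient in both arms;
- a date beside each wound field of item 35, so that a NO is tied to an examination and the time-to-event analysis has something to work from.

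The Group A sentence should also say whether its one-week timing covers wound outcomes or only the film. Arm-specific wound care stays as the protocol sets it; only the timing and recording of outcome assessment change.

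The cost is a few sentences of text, a date field and a few minutes' inspection per patient. No visit is added, because both arms already have a film at one week.

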#### 5) Follow up and treatment adherence

The patients in both groups will be followed up once every month for atleast three consecutive months assessing for evidence of wound infection, pain control and with chest radiography for evidence of pneumothorax. The wound will also be assessed for development of raised or elevated thoracostomy wound scars (unsightly scars appearing like hypertrophic scars or keloids) within 3 months of chest tube removal.

Patients with wound infection will have 10% povidone iodine daily dressing with institution of antibiotic therapy as per unit protocol. All patients with poor pain control (Pain score greater than 5),

involved with in this study, will have their pain control drug regimen escalated as per unit protocol to achieve better pain control.

#### DATA ANALYSIS AND MANAGEMENT

The data will be entered into the computer and thorough data cleaning will be done to check for errors and omissions at the end of data collection. The data was analyzed using Statistical Package for Social Sciences (SPSS) version 21. Descriptive statistics for baseline data shall be analyzed using mean, standard deviation, range and median, where appropriate, for any continuous variable and as percentages for any categorical variable. Baseline characteristics of the two study arms will be compared using Chi-square tests (for categorical variables) and student's t-test or analysis of variance (for continuous variables). Risk of complication will be evaluated using Cox-proportional analysis adjusting for potential confounders. Level of significance will be set at 5%. Findings will be presented in forms of texts, tables, figures and graphs as appropriate.

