# STUDY VARIABLES AND DEFINITION

The independent variables to be employed for the analysis include:

- Age of the patient
- Sex of the patient
- Presence of specific co-morbidities (Diabetes, Hypertension, Chronic Liver disease, Chronic kidney disease)
- Charleson Comorbidity Index
- History of cigarette smoking and estimated pack years if positive

- Use of steroids and chemotherapeutic agent
- Abnormal Body mass index (Obesity(BMI> 30kg/m^2), Malnutrition(BMI< 18kg/m^2)

The Dependent variables to be employed for the analysis include:

- Presence of severe pain at the chest tube site after chest tube insertion (Average daily pain score after tube insertion > 5 on the Visual Analog Scale and or Numerical Rating Scale)
- Occurrence of tube dislodgement after chest tube insertion
- Occurrence of peri-tubal leakage of fluid after chest tube insertion
- Presence of wound air suck-in after chest tube removal (indicated by presence of air suck-in sound through the wound into the pleural space during quiet and or forced inspiration)
- Occurrence of wound infection after chest tube removal (presence of purulent or offensive wound discharge with or without fever or presence of wound discharge that is microbiologically positive)
- Occurrence of wound dehiscence after chest tube removal
- Occurrence of early (within 7 days) and late pneumothorax (more than 1 week) after chest tube removal confirmed on chest radiography
- Development of raised or elevated thoracostomy wound scars (unsightly scars appearing like hypertrophic scars or keloids) within 3 months of chest tube removal

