#### SAMPLE SIZE

The sample size will be calculated by comparing the known incidence rate of 6% for acute pneumothorax when a purse- string suture is used and an incidence rate of 1.2% when the wound edges were un-reapproximated since the occurrence of pneumothorax is the most common morbidity or complication that is documented in the literatures (16). Using the software WinPepi (44), 142 subjects grouped into 71 subjects in group A and 71 subjects in group B will be required to compare a proportion rate of 6% in group A and 1.2% in group B, if level of significance is set at 5%, non-response rate set at 5% with the study powered at 80%; for a two-sided test.

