# EXCLUSION CRITERIA

Any patient so described above who has the following will be excluded:

- 1. An associated pyopneumothorax
- 2. Cancer encuirasse of the chest wall
- 3. Unconscious with unclear consent situation
- 4. With infective or neoplastic conditions of the chest wall
- 5. With individual or family history of wound failure e.g. unsightly scars
- 6. Who has had irradiation of the chest or chemotherapy administration within 6 weeks from the time of requirement of the chest tube insertion
- 7. Who is at risk of immunosuppression i.e. diabetes, HIV infection, on steroid therapy, ongoing chemotherapy or who has a congenital or any other acquired immune deficiency state
- 8. Presence of pleural adhesion during the process of chest tube insertion
- 9. Those with chest tube malposition after insertion, confirmed on chest radiograph, who will require tube adjustment

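### An adjusted Cox model is the only analysis named for complications, but the form records them undated and has no pneumothorax field after follow-up 1

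*Combined protocol and SAP*

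**What the plan says.** In Data Analysis and Management, the one sentence on outcomes reads: "Risk of complication will be evaluated using Cox-proportional analysis adjusting for potential confounders". The other tests in that section are tied to baseline: "Baseline characteristics of the two study arms will be compared using Chi-square tests (for categorical variables", with t-tests or analysis of variance for continuous variables. The section gives no time origin, event-time definition, censoring rule, covariate list or unadjusted comparison of complications.

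Study Variables and Definition lists outcomes as presence or occurrence, counted from different starting points. Some run from removal: "Occurrence of early (within 7 days) and late pneumothorax (more than 1 week) after chest tube removal confirmed on chest radiography". Others run from insertion: "Occurrence of tube dislodgement after chest tube insertion". The same section lists independent variables, including "Presence of specific co-morbidities (Diabetes, Hypertension, Chronic Liver disease, Chronic kidney disease" and "Use of steroids and chemotherapeutic agent". Exclusion Criteria, item 7, removes any patient "Who is at risk of immunosuppression i.e. diabetes, HIV infection, on steroid therapy, ongoing chemotherapy".

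Sample Size frames the trial as a comparison of two proportions, to "compare a proportion rate of 6% in group A and 1.2% in group B", with 71 patients per arm.

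The removal procedures for both groups plan chest films immediately after removal, at one week and at each clinic visit. Follow up and treatment adherence plans monthly visits for at least three months, with chest radiography for pneumothorax. The Study Proforma has yes/no pneumothorax boxes after insertion, for the immediate film, for the one-week film and at follow-up 1. The blocks for follow-ups 2 to 5 have none.

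**The concern.** A Cox model needs, for each patient, a time origin, an event or censoring time and an event indicator. The form supplies the indicator and only coarse timing. Whoever runs the analysis would have to choose origins, event times, a censoring rule and covariates after the data are in, in an open-label trial. For the outcome on which the trial is sized, events are so few that the model may give no usable estimate of the size of the difference.

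The missing pneumothorax boxes are a separate problem that would affect any analysis. Late pneumothorax is a listed outcome and films are planned to detect it, yet one first seen after follow-up 1 has nowhere to be written down.

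**Working it through.** **Timing: what a Cox model needs and what the form holds**

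| Needed | Available in the readable form |
|---|---|
| Time origin | Insertion for some outcomes and removal for others (Study Variables and Definition); not carried into the analysis section |
| Event time | Yes/no per period or visit; pneumothorax boxes tied to scheduled films; twice-daily pain scores for days 1 to 10 |
| Time at risk with the tube in place | Tube retention (item 32) |
| Censoring time | No visit or last-contact date |

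This is grouped data, and the plan has no rule for handling it. On the immediate post-removal film every event falls at one time. With 4 v 1 events at 71 per arm, the tied (Breslow) hazard ratio for Group B against Group A is 0.250, the same as the risk ratio (1/71)/(4/71) = 0.250. Cox adds nothing there.

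**Event counts**

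Inputs from Sample Size: 6% in Group A, 1.2% in Group B, 71 per arm, two-sided 5%, 80% power, 5% non-response. The 71 does not reproduce. With mean rate 0.036, the pooled formula gives [1.960 × √(2 × 0.036 × 0.964) + 0.842 × √(0.06 × 0.94 + 0.012 × 0.988)]² / 0.048² = 235.3, so 236 per arm, and 236/0.95 rounds up to 249. That is a separate matter; the figures below take the plan's rates and size as given.

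- Expected acute pneumothoraces: 71 × 0.06 = 4.26; 71 × 0.012 = 0.85; total 5.1.
- No event in Group A: 0.94^71 = 0.012. No event in Group B: 0.988^71 = 0.424.
- At least one arm empty: 1 − (1 − 0.0124)(1 − 0.4244) = 0.431. At 67 per arm, after 5% non-response, it is 0.454.

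The same probability under other conditions:

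| Condition | At least one arm empty |
|---|---|
| 6% v 1.2%, 249 per arm | 4.9% |
| 6% in both arms, 71 per arm | 2.5% |
| Wound infection, 7.7% (Literature Review) assumed in both arms, 71 per arm | 0.7% (142 × 0.077 = 10.9 events) |

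**An empty arm, for example 5 v 0**

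The hazard ratio has no finite estimate, and nor does the risk ratio of A to B. The tied score (log-rank) test is still defined: U = 5 − 2.5 = 2.5; V = 5 × 0.25 × 137/141 = 1.2145; chi-square = 2.5²/1.2145 = 5.15; p = 0.023. The risk difference is 5/71 = 7.0%, Newcombe 95% CI 0.5% to 15.4%. Fisher's exact test gives p = 0.058.

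**Power at 71 per arm, 6% v 1.2%, by full enumeration**

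Fisher 13.2%; unadjusted score test 32.3% (type I error 5.0% with 6% in both arms). Fisher's test and the Newcombe interval disagree about zero in 10.1% of trials.

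**Covariates**

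Diabetes is on the independent-variable list but excludes a patient, so it cannot vary among eligible patients. Current steroid therapy and ongoing chemotherapy are excluded too, so only past use could vary.

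**Pneumothorax fields**

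If follow-ups 1 to 3 are the minimum three monthly visits, films are planned at all three and only the first has a box. Two of the three planned films have no field.

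**The case against.** The strongest reply is that the 43% is borrowed. It depends on the rates and size in Sample Size, falls to 4.9% at 249 per arm, and reflects sparse data rather than a fault peculiar to Cox. That stands.

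A reader might infer that the model is unworkable for every complication. The documents do not support this. Wound infection at 7.7% would give about 11 events and almost never an empty arm. Retention time supplies follow-up time for event-free patients while the tube is in place, where unequal exposure makes Cox reasonable. The ties argument covers only the immediate film, because early pneumothorax spans seven days.

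A reader might also divide 5.1 events by the seven covariate groups in Study Variables and Definition, get 0.73 per group, and call the model overfitted. The analysis section does not say that its confounders are that list, or whether complications are modelled singly or pooled. What is shown is under-specification.

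Nor do the documents show that late pneumothorax will be materially under-counted, or more so in one arm. The boxes are missing for both arms, follow-up 1 can record a late case, and the Literature Review cites a 0% late rate in an un-sutured series.

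It is also fair that an exact test costs power against the score test, and that proportions to three months need a rule for patients lost early. Neither rescues the analysis as written: event times, origins and censoring remain undefined.

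**Conclusion.** The concern holds in two limited parts.

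First, the only named analysis of complications cannot be carried out as written without assigning event times, origins and censoring after the fact. For the immediate film it offers nothing beyond a comparison of proportions. For acute pneumothorax there is a 43% chance of no finite hazard ratio, conditional on 6% v 1.2% and 71 per arm; the figure is not a general property of the trial's outcomes.

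Second, the form has no place for a pneumothorax first seen at follow-ups 2 to 5, although films are planned then and late pneumothorax is a listed outcome. The size of the loss is unknown.

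Both rest on the readable form; the follow-up blocks are intact in it. The point should be fixed, but it is not by itself fatal, since the yes/no data support a simpler analysis. Low power is a separate sample-size problem.

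**What to change.** 1. Add a yes/no pneumothorax field at follow-ups 2 to 5.
2. Replace Cox as the main analysis. For each complication, compare by arm the proportion of patients affected in the periods the form records: tube in place (with retention time reported by arm), removal to 7 days, and to 3 months. Report the risk difference with a score-type 95% CI and one prespecified test, unadjusted for rare outcomes such as pneumothorax. The choice of test is the sponsor's; if test and interval can disagree, as Fisher and Newcombe do, state in advance which governs.
3. State whether the one-week film counts as early or late pneumothorax, and the denominator for patients lost before 3 months.
4. If Cox is kept for a commoner outcome, add removal, visit and event dates and define origin and censoring for that outcome.
5. Limit adjustment to common outcomes, with a short named covariate list that omits diabetes.

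The cost is revised analysis wording and one box on each of four visit blocks, plus date fields only if Cox is kept. The price is no event-timing information, no adjustment for rare outcomes and, with an exact test, lower power than a score test (Fisher 13% v 32% at the plan's rates and 71 per arm).

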# **STUDY HYPOTHESIS**

NULL HYPOTHESIS: There is no difference in the wound and clinical outcomes of patients who had purse-string (suturing with U- technique) for closure and those who had an occlusive adhesiveabsorbent dressing application (Un-reapproximated wound edges); for post-tube removal management of thoracostomy wound

ALTERNATE HYPOTHESIS: There is a major difference in the wound and clinical outcomes of patients who had purse-string (suturing with U- technique) for wound closure and those who had an occlusive adhesive-absorbent dressing (Un-reapproximated wound edges); for post-tube removal management of thoracostomy wound

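### No primary outcome, multiplicity method or rule for rejecting the joint null is stated, so the single 5% level does not fix the trial's false-positive risk.

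*Combined protocol and SAP*

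**What the plan says.** **Hypothesis.** The Study Hypothesis section gives one null for everything: "There is no difference in the wound and clinical outcomes of patients who had purse-string" closure and those who had the dressing. The alternative speaks of a major difference in the same undivided set of outcomes.

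**Outcomes.** Under Study Variables and Definition, "The Dependent variables to be employed for the analysis include" introduces eight bullets: severe pain, tube dislodgement, peri-tubal leakage, wound air suck-in, wound infection, dehiscence, early and late pneumothorax, and raised scars. One bullet holds two pneumothorax outcomes, so eight bullets make nine outcomes. None is ranked. The summary, objectives and research questions group outcomes but do not rank them either.

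**Sizing.** The Sample Size section uses acute pneumothorax to "compare a proportion rate of 6% in group A and 1.2% in group B". The design is two-sided at the 5% level, with 80% power and a 5% allowance for non-response. The reason given for the choice is "since the occurrence of pneumothorax is the most common morbidity or complication that is documented in the literatures". It is not called primary.

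**Analysis.** Data Analysis and Management has one sentence on outcomes, a Cox analysis of the risk of complication adjusted for potential confounders. It then says "Level of significance will be set at 5" per cent. No composite, testing order, multiplicity adjustment or rule for rejecting the joint null appears there or elsewhere.

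**The concern.** A 5% level describes a trial's error rate only when it is attached to one test, or to a family of tests with a rule that controls the family. Here it is attached to neither. A reader who follows the plan can take a small p-value on any listed outcome as evidence against the stated null, and nothing in the text prevents this.

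Two features raise the stakes. The trial is open-label, and some outcomes, such as pain and scar appearance, involve judgement. The study summary also says the data will supply a general guideline and shape the institutional protocol, so a chance finding could affect practice.

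**Working it through.** **Inputs.** Two-sided 5% level, 80% power, 5% non-response, 6% versus 1.2%, and "71 subjects in group A and 71 subjects in group B" (Sample Size). Eight bullets or nine outcomes (Study Variables and Definition). One analysis per outcome is an assumption, because the plan does not say so.

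**1. The plan's own figure.** With mean rate 0.036 and difference 0.048, the usual pooled formula is

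n per arm = [1.960·√(2·0.036·0.964) + 0.842·√(0.06·0.94 + 0.012·0.988)]² / 0.048² = (0.5164 + 0.2199)² / 0.002304 ≈ 235.3, so 236.

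With 5% non-response, 236/0.95 gives 249 per arm. The stated 71 per arm is not reproduced. Continuity-corrected (276), unpooled (233), arcsine (207) and one-sided (186) versions, before non-response, do not come near it.

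Power at 71 per arm = Φ[(0.048·√71 − 0.5164)/0.2613] = Φ(−0.428) = 33%. Exact enumeration gives 32% for chi-square and 13% for Fisher.

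**2. Family-wise error, independent tests of true size 5%.**

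- Nine tests: 1 − 0.95⁹ = 37.0%
- Eight tests: 1 − 0.95⁸ = 33.7%

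The upper bounds under any dependence are 9 × 5% = 45% and 8 × 5% = 40%.

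**3. Correlation.** Simulating nine two-sided tests with an assumed equal correlation gives 34.8% at 0.2, 32.6% at 0.3, 26.8% at 0.5 and 16.5% at 0.8.

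**4. Rare events.** With few events a nominal 5% test rejects less often than 5%. The table gives exact size s at 71 per arm with the same true rate in both arms, then 1 − (1 − s)⁹ for nine independent tests. The common rates are assumptions. They span values near those the literature review cites: 1.2% to 1.6% for individual complications with the dressing, and 6% as the lower end for pneumothorax with purse-string sutures.

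| Event rate for all nine | Chi-square size | Nine chi-square tests | Fisher size | Nine Fisher tests |
|---|---|---|---|---|
| 1.2% | 0.9% | 8% | 0.02% | 0.2% |
| 1.6% | 1.7% | 15% | 0.06% | 0.6% |
| 3% | 4.1% | 32% | 0.5% | 4.6% |
| 3.6% | 4.5% | 34% | 0.8% | 7.0% |
| 6% | 5.0% | 37% | 1.7% | 14% |

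**5. What this does not cover.** The plan assigns chi-square tests to baseline comparisons and Cox analysis to complications, and does not mention Fisher tests. The table shows how far rarity moves the answer. It does not give the error rate of the planned Cox tests, which were not modelled.

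**The case against.** **One test per outcome is inferred.** The analysis sentence refers to risk of complication in the singular and could mean a single any-complication model. That stands as a caveat. But no composite is defined and the outcomes are listed separately for the analysis, so one analysis per outcome is the natural reading.

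**No rule says that any p<0.05 rejects the null.** This also stands. A reader might infer that the plan has adopted such a rule, but the documents do not say so. The defect is that no decision rule is stated at all.

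**Acute pneumothorax may be an implicit primary outcome, because it sizes the trial.** That is a fair reading of the Sample Size section alone. However, neither the hypothesis nor the objectives are tied to it, and its bullet stands seventh of eight in an unranked list.

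**The count is soft.** Counting by bullets lowers 37% to 34%. In the other direction, the research questions add a pain-score comparison after removal, and the proforma records empyema, air leak and repeated visits. The conclusion does not depend on the exact count.

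**The inflation may be small.** If all outcomes were as rare as the dressing figures, the error could be modest, and with exact tests below 5%. That stands as a limit on the size. It is unlikely for all nine, since the literature review cites 7.7% for wound infection and 6% to 10.7% for pneumothorax with purse-string sutures.

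**Conclusion.** The omission is confirmed. With one joint null, nine unranked outcomes and one unadjusted 5% level, the plan does not determine its own false-positive risk.

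Given one analysis per outcome, and any p<0.05 counted against the null, the risk is up to about 37% for nine independent tests of true size 5%. For chi-square tests at 71 per arm it runs from about 8% (all rates 1.2%) to 37% (all rates 6%). Positive correlation lowers these figures. Fisher tests give 0.2% to 14% over the same rates, below 5% when all rates are 3% or less.

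Two stronger readings should be resisted. A reader might take 37% as the trial's actual error rate. It is the figure for independent tests at full nominal size, and neither condition is established here. A reader might also infer that the headline will come from a secondary outcome because the sizing outcome is underpowered. The low power is real, but no text in the plan supports a forecast of how results will be reported.

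**What to change.** **Change.** In Study Hypothesis and in Data Analysis and Management, name acute pneumothorax as the single primary outcome, tested two-sided at 5%, and tie the trial's conclusion to it. Define it as early pneumothorax, within 7 days of tube removal and confirmed on chest radiograph. State which films count: Sample Size says acute, Study Variables says within 7 days, and the proforma has separate immediate and one-week items.

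Report all other outcomes as secondary, as effect estimates with 95% confidence intervals and no confirmatory claim. If claims on them are wanted, Holm's procedure over the other eight would do. Its first step is 0.05/8 = 0.00625.

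**Cost.** The edit is to wording, but it has two consequences that the plan should state. An isolated secondary p<0.05 can no longer support a confirmatory claim. And the primary test has only about 32–33% power for 6% versus 1.2% at 71 per arm, so a non-significant result must not be read as no difference.

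The conflict between 71 per arm and the stated 80% power (236 per arm, or 249 with non-response) is a separate error and needs its own correction. Dividing alpha over nine outcomes instead (0.05/9 = 0.0056 each) would cut power for this outcome to about 11% at 71 per arm.
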